1. INTRODUCTION AND OBJECTIVES OF ANALYSIS

1.1. Introduction

TOGETHER trial is an adaptive platform trial for treating persons with early severe acute respiratory syndrome coronavirus 2 (SARS-CoV-2) infection at high risk of disease progression who do not require hospital admission. The TOGETHER trial will start with a placebo as a control in the clinical evaluation of fluvoxamine, ivermectin, and metformin. Other affordable candidate drug regimens that can be repurposed for coronavirus disease 2019 (COVID-19) may be considered and incorporated into this trial as an additional arm (s). If an intervention is shown to be effective, this design will allow the replacement of the placebo group with the effective intervention as the comparator.

1.2. Objectives of Statistical Analysis

This statistical analysis plan (SAP) is designed to outline the methods to be used in the analysis of study data to answer the study objective(s). We provided the populations for analysis, data handling rules, statistical methods, and data presentation formats. The statistical analyses and summary tabulations described in this SAP will provide the basis for the results sections of the clinical study report (CSR) for this trial.

2. STUDY DESIGN

2.1. Synopsis of Study Design

TOGETHER trial is an international multicenter adaptive randomized platform trial for the early treatment of SARS-CoV-2 infection in high-risk adults not requiring hospital admission. Initially, TOGETHER Trial will start with a placebo as a control in the clinical evaluation of fluvoxamine, ivermectin, and metformin. This trial is designed as a platform trial design that can add new arms

Statistical Analysis Plan

Sponsor:	McMaster University		
Protocol:	TOGETHER trial		
Document Version No.:	1.1	Document Date:	05-May-2021

onto the trial under standardized eligibility criteria, outcomes, and measurements, as the other experimental interventions. Other affordable candidate drug regimens that can be repurposed for COVID-19 may also be considered for this trial. The decision to add new therapeutic strategies will be based on external findings with local stakeholders' consultations.

2.2. Randomization Methodology

Eligible participants will be randomized at an equal allocation ratio to study experimental intervention(s) or placebo. Individual randomization will be stratified by clinical site, by age (<50 years vs. ≥50 years), and time from onset of symptoms (<120 hours vs. ≥120 hours). The randomization sequence for each clinical site will be prepared by the unblinded statistician and will be sent to the unblinded pharmacist at each participating clinical site. Allocation of treatment assignment will be concealed from all other study personnel.

2.3. Stopping Rules and Unblinding

Stopping rules are outlined in section 4.3. In the case of potential recruitment challenges, it is important to reach statistical conclusions about the experimental treatments as fast as possible; therefore, continual Bayesian learning methods have been prepared and simulated to prepare for potential protocol changes. These simulation results are described in section 4.3.

2.4. Study Procedures

As outlined in the study protocol, the schedule of assessment is provided in Table 1.

Statistical Analysis Plan

Sponsor:	McMaster University		
Protocol:	TOGETHER trial		
Document Version No.:	1.1	Document Date:	05-May-2021

Table 1. Schedule of Study Activities

	Screening and Treatment Period ⁹								Post-treatment Period ⁹			
	Screening Visit (D-0)	Baseline and Randomization (1) D-0	Day 1	Day 2 ⁽⁴⁾	Day 3 ⁽⁴⁾ ± 1 day	Day 4 ⁽⁴⁾	Day 5 ⁽⁴⁾	Day 7 ⁽⁴⁾ ± 1 day	Day 10 ± 2 days	Day 14 ⁽⁴⁾ ± 2 days	Day 28 ⁽⁴⁾ ± 3 days	Day 60 ^(4,8) or Early Termination ± 5 days
Informed Consent	X											
SARS-CoV2 Rapid Test	X ⁽¹⁾											
Eligibility Criteria Review	X ⁽²⁾											
Pregnancy Test	X ⁽³⁾											
Demographics	X ⁽⁵⁾											
Co-morbidities and Risk Factors	X											
Medical History	X											
WHO Clinical Worsening Scale	X		X	X	X	X	X	X	X	X	X	X
Temperature, Arterial O ₂ Saturation		X										
Exposure to Index Case Information		X										
Substance Abuse		X										
PROMIS Global Health Scale		X ⁽⁶⁾								X ⁽⁶⁾	X ⁽⁶⁾	X ⁽⁶⁾
ECG		X										
Height and Weight		X										
Nasopharyngeal Swab		X			X			X				
Randomization		X										
Concomitant Medications		X	X	X	X	X	X	X	X	X	X	X
Investigational Treatment Administration			X ⁽⁷⁾	X ⁽⁷⁾	X ⁽⁷⁾	X ⁽⁷⁾	X ⁽⁷⁾	X ⁽⁷⁾	X ⁽⁷⁾			

Statistical Analysis Plan

Sponsor:	McMaster University		
Protocol:	TOGETHER trial		
Document Version No.:	1.1	Document Date:	05-May-2021

Hospitalization / Emergency Room Visits			X	X	X	X	X	X	X	X	X	X
Respiratory Symptoms			X	X	X	X	X	X	X	X	X	X
Adverse Events			X	X	X	X	X	X	X	X	X	X
Adverse Drug Reactions			X	X	X	X	X	X	X	X	X	X
Vaccination Status										X	X	X

Legend

1. Screening and baseline visit: must be carried out at the same time when attending the outpatient setting. Rapid antigen test for COVID-19 at the screening visit. Day 1 visit should also be conducted on the same day as the screening and baseline visit. After completing the screening visit procedures at the baseline visit and present all inclusion / exclusion criteria, participants should be immediately randomized. The first dose of treatment under investigation must be administered on the same day of randomization (immediately after randomizing). The study medication will be administered as prescribed. Patients must be observed for 30 minutes after the medication administration.
2. Patients can be included in the trial if they have a COVID-19 diagnosis at baseline visit and have less than 7 days of flu-like symptoms.
3. Only women of childbearing potential and / or potential to become pregnant. Women of childbearing potential must necessarily use contraception during the first 15 days of the trial.
4. Visits through telephone contact, video call, telemedicine are calculated from the randomization date.
5. After signing the Informed Consent Form.
6. Questionnaires must be completed BEFORE any procedures of the proposed visit. Only a person not related to the research can help the patient during the questionnaire. In telephone visits, the patient must respond directly, at the time of contact.
7. Maintain the administration of the product under investigation according to schedule. Discontinue it if adverse events prevent the medication from continuing.
8. Assessment of late complications associated with COVID-19.
9. Unscheduled visits may also be conducted as needed. The clinical outcome data collected at the unscheduled visit should be entered at the next scheduled visit. The treatment period is up to 10 days.

Statistical Analysis Plan

Sponsor:	McMaster University		
Protocol:	TOGETHER trial		
Document Version No.:	1.1	Document Date:	05-May-2021

2.5. Efficacy and Safety Variables

2.5.1. Efficacy Variables

Primary endpoint:

- Emergency room visit due to the clinical worsening of COVID-19 (defined as participants remaining under observation for > 6 hours) within 28 days of randomization
- Hospitalization due to the progression of COVID-19 (defined as worsening of viral pneumonia) and/or complications within 28 days of randomization

Secondary endpoints:

- Viral clearance and viral load on D3 and D7 after randomization;
- Time (in days) to clinical improvement (up to 28 days of randomization), defined as the first day on which the participants report a score of 0 on the World Health Organization (WHO) Clinical Worsening Scale;
- Time (in days) to clinical failure;
- Number of days with respiratory symptoms since randomization;
- Hospitalization for any causes;
- Time to hospitalization due to COVID-19 progression;
- Mortality due to pulmonary complications;
- Mortality due to cardiovascular complications;
- Mortality from any causes;
- Adverse events that occurred (up to 28 days);
- Adverse drug reactions;
- WHO clinical worsening scale over the follow-up period;
- WHO clinical worsening scale during the treatment phase;
- PROMIS global health scale scores (days 14 and 28).

Statistical Analysis Plan

Sponsor:	McMaster University		
Protocol:	TOGETHER trial		
Document Version No.:	1.1	Document Date:	05-May-2021

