4.2.8. Visit Windows

Table 1 Evaluation Intervals for Efficacy Analysis

Evaluation	Protocol-Specified Interval	Interval for Analysis
Baseline	Day 0	Day 0 to Day 1
Treatment period	Day 1 to 3 or Day 1 to Day 10	Day 0 to Day 10 (Day 3 and Day 7 \pm 1 day)
End-of-Therapy	Day 3 or Day 10	Day 10 (\pm 2 days)
Post-Treatment	Day 11 to Day 60	Day 14 (\pm 2 days); Day 28 (\pm 3 days); Day 60 (\pm 5 days)

Actual dates and times will be used for pharmacokinetic analyses rather than nominal days and times.

Statistical Analysis Plan

Sponsor:	McMaster University		
Protocol:	TOGETHER trial		
Document Version No.:	1.1	Document Date:	05-May-2021

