4.6. Efficacy Evaluation

Efficacy analysis will be conducted using the ITT and PP Populations as outlined below. The two primary endpoints will be analyzed as a composite. Secondary endpoints will be assessed within 28 days of randomization, unless stated differently.

Table 3: Objectives and Endpoints

Objectives	Endpoints
Primary	

 Reduction in the need for emergency room visits due to the clinical worsening of COVID-19 and keeping the participant under observation for > 6 hours within 28 days of randomization in acutely affected patients and with evidence of high-risk for complications 	
 Proportion of those in need of emergency care under observation for more than 6 hours for COVID-19

 Reduction in the need for hospitalization due to the progression of COVID-19 (worsening of viral pneumonia) or complications within 28 days of randomization in acutely affected patients and with evidence of high-risk for complications 	
 Proportion of those in need of hospitalization due to progression of COVID-19 and/or complications
Secondary	

 To test the efficacy of experimental interventions to reduce SARS-CoV-2 viral shedding at day 3 and day 7 	
 Proportion of persons with clearance of SARS-CoV-2 from nasal swabs or saliva, defined as 1 negative swab Proportion of days with SARS-CoV-2 detected from mid-nasal swabs by PCR Change in viral load on day 3 and day 7 compared to baseline

 To test whether any of the experimental interventions decrease time to resolution for symptomatic SARS-CoV-2 infection / COVID-19 disease 	
 Time to clinical improvement (up to 28 days of randomization), defined as the first day on which the participant reports a score of 0 on the WHO Clinical Worsening Scale

Statistical Analysis Plan

Sponsor:	McMaster University		
Protocol:	TOGETHER trial		
Document Version No.:	1.1	Document Date:	05-May-2021

	
 • Time to clinical failure • Number of days with respiratory symptoms after randomization • Proportion of patients on each scale of the WHO clinical worsening scale over the treatment period and over the follow-up period

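### Time to clinical improvement treats contact days as exact recovery days across a 14-day gap in the WHO scale, and its 28-day limit is not reconciled with the Day 25 to 31 analysis interval

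*SAP*

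**What the plan says.** - **Endpoint.** SAP 2.5.1 places this among the secondary endpoints and limits it to the first 28 days. The event is "defined as the first day on which the participants report a score of 0 on the World Health Organization (WHO) Clinical Worsening Scale". Table 3 in section 4.6 repeats it: "Time to clinical improvement (up to 28 days of randomization), defined as the first day on which the participant reports a score of 0".
- **Schedule.** In the schedule of study activities (section 2.4), the row "WHO Clinical Worsening Scale" is marked after randomization on Days 1, 2, 3, 4, 5, 7, 10, 14, 28 and 60.
- **Unscheduled contacts.** Note 9 to that schedule says "Unscheduled visits may also be conducted as needed". On where such data go, it adds: "The clinical outcome data collected at the unscheduled visit should be entered at the next scheduled visit".
- **Analysis intervals.** Section 4.2.8 gives, for the post-treatment period, "Day 14 (\pm 2 days); Day 28 (\pm 3 days); Day 60 (\pm 5 days"). The Day 28 evaluation thus runs from Day 25 to Day 31.
- **Model.** Section 4.2.3.2 uses a proportional hazards model with a piecewise-constant baseline hazard. Each observation is either an event at a known time or right-censored. Section 4.2.1 summarizes time-to-event data with Bayesian Kaplan-Meier estimates. Neither section provides for interval censoring.

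**The concern.** The day on which a patient first reports a 0 is the day someone asked, unless a recovery date is collected in some other way. Early on this matters little, because contacts are one to four days apart. Then nothing is scheduled for the second half of the 28-day period. A patient who recovers on Day 16 and one who recovers on Day 27 both first report a 0 at the Day 28 contact. The plan's methods read that day as the recovery day.

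Unscheduled visits do not clearly close the gap, since their outcome data are entered at the next scheduled visit. The endpoint also stops at 28 days while the last relevant contact may fall up to three days later, and no rule says which of the two governs.

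At stake are the recovery curve, the median time to improvement in each arm, and any reading of how many patients had improved by Day 28.

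**Working it through.** The SAP gives no event rate, power or median for this endpoint, so there is no stated figure to reproduce.

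**Inputs from the SAP.** Contact days 1, 2, 3, 4, 5, 7, 10, 14, 28; windows ±1 at Days 3 and 7, ±2 at Days 10 and 14, ±3 at Day 28; endpoint limit 28 days.

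**Assumptions not in the SAP.** Exponential recovery with median m, so S(t) = 2^(−t/m); the score stays at 0 once reached; contacts uniform on whole days within their windows; none missed.

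**1. Size of the gap.** Successive gaps up to Day 28 are 1, 1, 1, 1, 2, 3, 4 and 14 days. With windows, the last gap runs from 25 − 16 = 9 to 31 − 12 = 19 days. The largest delay is therefore 14 days on nominal days and 19 days with windows (28 − 12 = 16 if cut at Day 28).

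**2. Patients affected.** The share recovering between Days 14 and 28 is S(14) − S(28). For m = 14 this is 0.50 − 0.25 = 25%; for m = 7, 0.25 − 0.0625 = 19%; for m = 21, 0.630 − 0.397 = 23%.

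**3. Mean delay for those patients, nominal days.** With λ = ln 2 / m and e = exp(−14λ), the mean delay is 14 − [1/λ − 14e/(1 − e)]. For m = 14: 14 − [20.2 − 14 × 0.5/0.5] = 7.8 days. For m = 7 it is 8.6 and for m = 21 it is 7.5.

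**4. Recorded median** (simulation, 400,000 patients per scenario).

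| True median | Recorded, contact dates with windows | Recorded, nominal days |
|---|---|---|
| 7 | 8 | 7 to 10 |
| 14 | 25 | 28 |
| 21 | 29 | 28 |

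The middle row can be checked by hand. Averaged over a Day 14 contact on Days 12 to 16, S = 0.501, so 49.9% have reported a 0 by that contact. A Day 28 contact on Day 25 (probability 1/7) adds (0.501 − 0.290)/7 = 0.030, giving 52.9%. The recorded median is Day 25. On nominal days a true median of exactly 14 lies on the boundary, and any value slightly above it is recorded as 28.

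**5. Difference in medians at an assumed hazard ratio of 1.3** (contact dates). The true gain is m − m/1.3.

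| Control median | True gain | Recorded gain |
|---|---|---|
| 10 | 2.3 | 2 |
| 12 | 2.8 | 3 |
| 13 | 3.0 | 4 |
| 14 | 3.2 | 12 |
| 18 | 4.2 | 11 |

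**6. Hazard ratio.** Refitted with a piecewise-constant hazard, the assumed 1.30 becomes 1.27 (m = 7) to 1.28 (m = 14 and 21). In a separate simulation with 681 per arm and m = 14, it moved from 1.317 with exact times to 1.298 with recorded times.

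**7. Recovered by Day 28 but counted as not improved.** Two routes, for m = 14:
- Day 28 contact on Days 29 to 31 (probability 3/7) and cut off: 3/7 × (0.501 − 0.250) = 10.8%.
- Recovery after an early Day 28 contact on Day 25, 26 or 27: (0.040 + 0.026 + 0.013)/7 = 1.1%.

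If contact dates are cut at Day 28, both apply, giving 11.9%. If any Day 25 to 31 contact counts as Day 28, only the second applies, giving 1.1%. For m = 7 the two totals are 8.7% and 0.6%; for m = 21 they are 11.2% and 1.2%. If every contact falls exactly on Day 28, the share is 0%.

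**The case against.** - **Inference rests on the treatment coefficient, not on medians.** Section 4.2.3.2 bases efficacy on the credible interval for that coefficient, and both arms share one schedule. This stands: step 6 shows little attenuation. The harm is to the description of recovery times, not to the direction of the comparison.
- **Section 4.2.8 may already settle the Day 29 to 31 contacts.** Its table is headed as intervals for efficacy analysis, and it reserves actual dates for pharmacokinetic analyses. Nominal days for efficacy are then a fair reading, and the miscounted share is about 1%. But the endpoint definition still carries a 28-day limit, and the SAP does not say which rule prevails.
- **A recalled recovery date is not excluded.** True; the case report form is not at hand. But the SAP mentions no such date, and a day of first report reads most naturally as the contact day.
- **A large false gain in medians is tempting but scenario-bound.** A reader might infer from step 5 that a gain of about 3 days will appear as 12. That happens only when the control median is about 14 to 18 days, so that the two medians fall on either side of the gap. The SAP gives no recovery rate.
- **Relapse and death.** A reader might add that a single 0 followed by admission should not count, or that deaths are censored and so credited. The first swaps in a different endpoint; later deterioration is captured by the primary composite, time to clinical failure, hospitalization and mortality. The second supposes a rule for deaths that the SAP does not state. The same holds for "Number of days with respiratory symptoms since randomization": how deaths and days between contacts are counted is not given, so no error can be shown.

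**Conclusion.** The point holds for the recorded recovery times. The day of first report is analysed as exact although half of the 28-day period has no scheduled assessment. About 19 to 25% of patients would recover in that stretch and, on nominal days, be recorded a mean of 7.5 to 8.6 days late. A median near or beyond Day 14 is seriously overstated; a median near 7 is not. These figures rest on exponential recovery with medians of 7 to 21 days, uniform contact timing and no missed contacts.

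A reader might infer that the gap itself turns recovered patients into failures. It does not: someone who recovers on Day 18 and is contacted by Day 28 counts as improved, only late. The 9 to 12% arises from cutting contact dates at Day 28, a rule the SAP neither adopts nor excludes.

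This is one secondary endpoint. The primary endpoint, sample size and stopping rules are not touched.

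**What to change.** 1. In sections 2.5.1 and 4.6, state that time to clinical improvement is interval-censored between the last contact with a score above 0 and the first contact with a score of 0.
2. In section 4.2.3.2, replace the event contribution for this endpoint by S(left) − S(right), with S the survival function of the piecewise-constant hazard model already specified. Patients with no reported 0 stay right-censored at their last contact.
3. In section 4.2.1, replace the Kaplan-Meier summary for this endpoint by an interval-censored estimate of the recovery curve and median.
4. In section 4.2.8, state that a Day 28 contact made on Days 29 to 31 supplies the right end of the interval. This reconciles the visit window with the 28-day limit, because the curve can then be read at Day 28 without discarding those contacts.

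The cost is SAP wording, a small change to the likelihood code and slightly wider credible intervals. No visit, sample size or primary analysis changes.

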2.5.2. Safety Variables

Safety assessments performed during the study included measurement of vital signs and monitoring of adverse events and adverse drug reactions.

3. SUBJECT POPULATIONS

3.1. Population Definitions

The following subject populations will be evaluated and used for presentation and analysis of the data:

- Intent-to-treat (ITT) Population: The ITT Population includes all randomized patients.
- Per-protocol (PP) Population: Randomized patients who adhered to more than 80% of the assigned therapy.
- Safety Population: Randomized patients who received at least 1 dose of study medication.

The ITT Population is typically the primary population for the analysis of efficacy parameters. A subset of efficacy parameters will be evaluated for the PP population (see Section 4.6).

The Safety Population is typically the primary population for the analysis of safety endpoints.

3.2. Protocol Violations

At the discretion of the sponsor, major protocol violations as determined by a review of the data prior to unblinding of the study results and the conduct of statistical analyses may result in the removal of a subject's data from the per-protocol population.

The sponsor, or designee, will be responsible for producing the final protocol violation file (formatted as a Microsoft Excel file), in collaboration with Cytel and the data monitoring group as applicable; this file will include a description of the protocol violation, and clearly identify

Statistical Analysis Plan

Sponsor:	McMaster University		
Protocol:	TOGETHER trial		
Document Version No.:	1.1	Document Date:	05-May-2021

whether or not this violation warrants exclusion from the Efficacy Evaluable Population. This file will be finalized prior to hard database lock.

All protocol violations will be presented in the data listings. The major protocol violations will include:

- Failure to obtain informed consent prior to initiation of study-related procedures
- A research subject met withdrawal criteria or wished to withdraw from the study but was not withdrawn
- Inappropriate study drug dosage
- Inappropriate randomization
- Inadvertent loss of samples or data
- Other major violation

The minor protocol deviations include:

- Concomitant medication
- Non-compliance to study procedures
- Visit made outside of the visit window

4. STATISTICAL METHODS

4.1. Sample Size Justification

The sample size of 681 patients per arm has been chosen for each experimental group to achieve 80% power with 0.05 two-sided Type 1 error for a pairwise comparison against the control to detect minimum treatment efficacy defined by 37.5% relative risk reduction (RRR) of preventing hospitalization assuming a control event rate (CER) of 15%.

Statistical Analysis Plan

Sponsor:	McMaster University		
Protocol:	TOGETHER trial		
Document Version No.:	1.1	Document Date:	05-May-2021

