APPENDIX

1. Interim analysis in an even-based Bayesian adaptive clinical trial

Suppose that we have I active treatments, such that

$$y_{ij}|p_i \sim \text{Binom}(n_{ij}, p_i), \quad i = 1, \dots, I,$$

where $j = 1, \dots, J$ denotes the number of interim analysis, n_{ij} is the number of patients randomized to the i^{th} arm, and p_i is the corresponding event rate. If we then assign a prior distribution

$$p_i \sim \text{Beta}(a, b),$$

Then by conjugation we obtain

$$p_i|y_{ij} \sim \text{Beta}(a + y_{ij}, b + n_{ij} - y_{ij}). \quad (1)$$

Control comparisons will then be based on *posterior efficacy*, namely

$$\Pr(p_i < p_{\text{ctrl}} | y_{ij}, y_{\text{ctrl}}),$$

which can be handily calculated by drawing independent Monte Carlo samples from the posterior distributions of the two arms using (1). Posterior inference on the relative risk reduction (RRR) can then be derived using the relationship

$$R_i = 1 - \frac{p_i}{p_{\text{ctrl}}}. \quad (2)$$

Proposed design for a 4-arm trial

- Perform interim analysis when 171, 342, and 513 patient outcomes have been recorded for each of the trial arms – corresponding to 25%, 50% and 75% of the maximum enrollment - and a final analysis when all 681 patient outcomes have been registered.
- Use $a = b = 1$ for beta prior distribution of all arms, corresponding to a uniform distribution.
- Stop early for efficacy if the posterior probability of efficacy exceeds 97.6%. The same test is conducted at the end of the trial if no early stopping rules are triggered.

Statistical Analysis Plan

Sponsor:	McMaster University		
Protocol:	TOGETHER trial		
Document Version No.:	1.1	Document Date:	05-May-2021

- Stop early for futility if the posterior probability of efficacy is smaller than 20% in the first analysis; 40% in the second analysis; 60% in the third analysis.

The operating characteristics of this design, as determined by 200,000 simulation runs, are as follows

Table 4: Operating Characteristics for the Proposed Bayesian Design

Arm	RRR	Power	Mean % of patients (SD)	Pr(Stop at 1)	Pr(Stop at <=2)	Pr(Stop at <=3)
1	37.50%	84.80%	64.1 (29.6)	25.20%	53.50%	73.80%
2	20%	30.70%	84.2 (26.0)	10.40%	23.90%	39.20%
3	0%	2.50%	71.1 (28.4)	16.80%	42.50%	67.00%

From Table 4 it is evident that the type I error rate of this trial design is 2.5% (one-sided). Note that a treatment with a relative risk reduction of 37.5% will – on average – require only two-thirds of the maximum sample size of 681.

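### Section 4.1 attributes 681 patients per arm to 80% power, but its stated inputs give about 89% (530 per arm would give 80%), and it names hospitalisation rather than the composite primary endpoint

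*SAP*

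**What the plan says.** Section 4.1 is the only place where the SAP justifies the number of patients: "The sample size of 681 patients per arm has been chosen for each experimental group to achieve 80% power with 0.05 two-sided" type I error. The error rate is "0.05 two-sided Type 1 error for a pairwise comparison against the control", and the effect is "37.5% relative risk reduction (RRR) of preventing hospitalization assuming a control event rate (CER) of 15" per cent. Section 2.2 sets the allocation: "Eligible participants will be randomized at an equal allocation ratio to study experimental intervention(s) or placebo".

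Section 4.1 states no allowance for dropout and no adjusted alpha. Section 4.2.7 expects outcomes on nearly everyone, and section 4.2.4 says that the placebo comparisons need no multiplicity adjustment.

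Section 4.3 and the appendix use the same 681, 15% and 37.5% in a four-look Bayesian rule: uniform priors, efficacy above 97.6%, futility below 20%, 40% and 60%. The appendix table headed "Table 4: Operating Characteristics for the Proposed Bayesian Design" reports 84.8% power and 2.5% one-sided type I error for that rule.

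On the endpoint, section 2.5.1 lists an emergency room visit with more than 6 hours of observation and COVID-19 hospitalisation, and section 4.6 says: "The two primary endpoints will be analyzed as a composite". Section 4.3.1 bases sample size re-assessment on hospitalisation or emergency room visit.

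**The concern.** Section 4.1 gives everything needed to check a two-proportion calculation: both rates, alpha, sidedness, allocation and size. The check misses the stated power by about 9 percentage points, more than a choice of formula explains. At least one of the printed figures (681, 80%, 15%, 37.5%, 0.05) is therefore wrong, or an input behind 681 has been left out.

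Which one matters. If the control rate really intended was lower than 15%, section 4.3 and the appendix simulate the design at a more favourable rate than the one that produced the size. If 15% was intended, the stated power is simply too low. The endpoint wording adds to the doubt, because the reader cannot tell whether 15% describes hospitalisation alone or the composite that is analysed.

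**Working it through.** **Inputs.** From 4.1: n = 681 per arm, two-sided alpha 0.05 (z = 1.960), target power 80% (z = 0.8416), control rate p1 = 0.15, relative reduction 37.5%. So p2 = 0.15 × 0.625 = 0.09375 and d = p1 − p2 = 0.05625. From 2.2: equal arms. The mean rate is m = 0.121875.

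**1. Power at 681 from these inputs (pooled formula).**

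z(power) = [d√n − 1.960 √(2m(1−m))] / √(p1(1−p1) + p2(1−p2))

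- d√n = 0.05625 × 26.096 = 1.4679
- 1.960 × √0.21404 = 0.9068
- √(0.1275 + 0.08496) = 0.4609
- z(power) = (1.4679 − 0.9068) / 0.4609 = 1.217, so power is **88.8%**

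The stated 80% is not reproduced. Other standard versions give 89.0% (unpooled), 89.1% (arcsine) and 87.2% (continuity-corrected). A single final look requiring a posterior probability above 97.6% gives 88.7%. Reading alpha as one-sided 0.05 moves further away, to 93.7%.

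**2. Size for 80% power from these inputs.**

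n = [0.9068 + 0.8416 × 0.4609]² / d² = 1.2947² / 0.003164 = 529.8, so **530 per arm** (527 unpooled, 565 continuity-corrected). The stated 681 is 151 more than 530, or 28%.

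**3. What would give 681?** Keep the 37.5% reduction and two-sided 0.05, and set the control rate to 12%. Then p2 = 0.075, d = 0.045 and m = 0.0975.

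- 1.960 × √0.17599 = 0.8222
- 0.8416 × √0.174975 = 0.3520
- n = (0.8222 + 0.3520)² / 0.002025 = 680.9, so **681**

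Other unstated inputs come near:

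| Unstated input | n per arm |
|---|---|
| Two-sided alpha 0.025, continuity-corrected | 677 |
| 20% dropout on 530 (530 / 0.8) | 663 |
| 15% dropout on 565 (565 / 0.85) | 665 |
| 565 × 1.20 | 678 |
| Bonferroni for three comparisons | 707 |

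Reaching 681 from 530 by dropout alone would take a loss of 1 − 530/681 = 22%.

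**4. Sensitivity to the control rate.** Fixed-sample power at 681 with a 37.5% reduction (10% and 12% are assumed rates):

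| Control rate | Power at 681 |
|---|---|
| 10% | 71.7% |
| 12% | 80.0% |
| 15% | 88.8% |

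**5. Can Table 4 supply the right figure?** The rule as written was simulated at a 15% control rate: uniform priors, looks at 171, 342, 513 and 681, efficacy above 97.6%, futility below 20/40/60%. Runs of 400,000 to 1,000,000 trials gave about 90.9% power at a 37.5% reduction and about 6.0% one-sided type I error. Table 4 reports 84.8% and 2.5%. That mismatch is a separate matter, but it means that 84.8% cannot yet replace the 80%.

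**6. Endpoint.** Section 4.1 speaks of "relative risk reduction (RRR) of preventing hospitalization assuming a control event rate (CER) of 15" per cent, sections 2.5.1 and 4.6 define and analyse a composite, and section 4.3.1 re-assesses on hospitalisation or emergency room visit. Sections 4.3 and the appendix use 15% without naming an endpoint.

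**The case against.** The strongest reply is that the error is harmless. On the stated inputs 681 gives more power than claimed, and no analysis or decision rule uses the 80%. Section 4.3 takes 681, 15% and 37.5% as inputs, and section 4.3.1 uses observed events and targets 90% predictive power. This stands, so a reader should not infer that interim or re-assessment planning starts from a wrong power figure.

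The 681 may also include a margin explained in the protocol, which is not at hand. That is possible, so a reader should not conclude that the trial enrols 151 patients per arm too many: this holds only if 15% was intended and no inflation was meant. It does not rescue 4.1, which attributes 681 to inputs that do not yield it.

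A reader might also set 80%, 84.8%, 88.8% and 90.9% side by side and say that one design has four powers. The SAP states only two of them. The 84.8% belongs to a four-look rule with futility stops and need not equal a fixed-sample figure, and the 90.9% comes from simulating the stated rule.

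Nor does an adjustment for three comparisons explain the size. A Dunnett-type critical value of 2.35 gives 684 to 688, not 681, and section 4.2.4 disclaims adjustment.

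On the endpoint, if 15% describes hospitalisation alone, the composite rate cannot be lower, and at the same relative reduction power would be no lower. So no loss of power is shown. The wording is still inconsistent, and the reduction assumed for the composite is not stated.

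**Conclusion.** Section 4.1 is wrong as written. Its inputs give about 89% power at 681 per arm (87.2% to 89.1% by method) rather than 80%, and 80% needs about 530 (565 with continuity correction). This rests only on figures in 4.1 and the equal allocation in 2.2.

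That 681 came from a 12% control rate is an inference: the arithmetic fits to the patient, but the SAP does not say so. Underpowering would follow only if the true rate were below about 12%, which nothing in the SAP states. The endpoint mismatch between 4.1 and 4.6 is plain on the page, though its effect on power cannot be calculated without a rate for the composite.

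This should be corrected because 4.1 is the SAP's sole justification for 681, and 681 fixes the timing of every interim look. It does not call the enrolment target into question on the stated inputs.

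**What to change.** In section 4.1:

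- Name the composite primary endpoint, and state the control event rate and relative reduction assumed for it. The SAP does not tie 15% to the composite, so the sponsor must confirm the rate.
- Correct whichever figure is wrong: the power (about 89% fixed-sample, if the control rate is 15%) or the control rate (12%, if 80% power is intended).
- State any dropout or alpha allowance behind 681.
- Say whether the quoted power is for a fixed-sample test or for the four-look rule of section 4.3.

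Then make 4.1, 4.3 and Table 4 agree. If the control rate changes, the simulations in the appendix must be rerun at that rate. Until the Table 4 simulation is reconciled with the stated thresholds, do not carry its 84.8% into 4.1. Nor should the 90.9% be adopted by itself, because the same rule then has about 6.0% one-sided error.

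The cost is a change to SAP text and a check of the existing simulation. Enrolment does not change.
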